The study will take place at OSUWMC. At OSUWMC there are approximately 13,000 hospitalizations with a diagnosis code for diabetes each year and current annual inpatient diabetes consult service and diabetes educator consults are roughly 3000 per year. OSUWMC has implemented a comprehensive, hospital-wide inpatient diabetes program since 2006, including streamlined computerized diabetes related order sets, carbohydrate-based insulin dosing, education, and ongoing review of outcomes. OSUWMC converted to EPIC EHR in 2011 for both inpatient and outpatient electronic medical records. The medical centers MICU has been utilizing Dexcom G6 CGM for COVID-19 patients since May of 2020 and to date has utilized CGM in over 132 critically ill COVID-19 patients. The study will take place in the MICU. The MICU is a 48-bed critical care center and employs 152 staff nurses. Patients will be identified through daily screening of patients and associated glycemic control in the MICU to identify potential participants with hyperglycemia (glucose >250mg/dl) or those currently on IV insulin. In 2019, prior to the COVID-19 pandemic, OSUWMC had 1,065 unique patient admissions in which the patient had a glucose >250mg/dl over the course of their MICU stay. Within the MICU patient population, patients with more severe illness and those with conditions that may interfere with CGM sensor accuracy will be excluded from participation. Full inclusion and exclusion criteria are as follows:

Eligible individuals are:

- 1) adults >18 years old,
- 2) admitted to OSUWMC MICU and

- 3) have hyperglycemia (glucose >250mg/dl) or are currently on IV insulin.

Non-eligible individuals are:

- 7) Current COVID-19 infection,
- 8) Refractory shock (Levophed dose >0.5 mcg/kg/min or equivalent)
- 9) Actively being treated for diabetic ketoacidosis (DKA)
- 10) Actively being treated for hyperosmolar non-ketoacidosis (HONK)
- 11) Pitting edema, anasarca, blue or purple discoloration to left upper extremity
- 12) Treated with high dose acetaminophen (>1 gram Q6 hours)
- 13) Treated with hydroxyurea
- 14) Are pregnant, patients
- 15) Using home insulin pump therapy during hospitalization, or
- 16) Reside in a corrections institution.

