Nurse training: OSUWMC MICU nurses have significant experience with CGM use in an extremely ill cohort of COVID-19 patients. Each nurse in the MICU receives training on CGM set-up, insertion, pairing, and CGM glucose monitoring features as part of their annual critical care competencies. OSUWMC MICU nurses are trained and experienced in using POC glucose measurement to validate the CGM system, however the protocol at use in this study differs somewhat from the COVID-19 protocol currently at use in the MICU. Given that, nurses will receive training on distinctions between the two protocols including changes to the frequency of POC testing, the addition of clinical status events that would warrant more frequent POC testing and validation (Q1 or Q2 hours depending on number of events present for a duration of 6 hours). New criteria to stop clinical use (i.e., no use of CGM for glucose monitoring, no use of CGM for insulin titration) will be reviewed in detail with nursing along with plans for the sensor to remain in place only for data collection. Nursing trainings will be conducted by PI ([name]), Co-I ([name]), and study coordinator during staff meetings and nursing huddles conducted on all shifts. All nurses will receive training on the new protocol prior to patient recruitment. The study protocol, along with currently available training materials, will be kept at the bedside of all patient participants.

Staggered enrollment and initial pilot: We will stagger enrollment with just 20 patient participants over a 4-week period (target 5 participants/week with a respite between enrollment to allow analysis of safety and fidelity data prior to the next round. A robust analysis would be conducted after this first “pilot” round of enrollment. Accuracy analysis would include MARD and Clark Error Grid. A full assessment of protocol adherence and evaluate adherence to standard insulin dosing guidelines will be completed. The pilot analysis will include evaluation of

benchmarks for accuracy, safety, and adverse event monitoring with benchmarks that must be met prior to subsequent enrollment. Pilot benchmarks for study continuation are as follows:

- Successful initial validation criteria within 24 hours in 80% of participants (16/20)
- Clark error grid analysis demonstrating >95% points in zone A (within 20% of reference glucose value) or zone B (outside of 20% but would not lead to inappropriate treatment) following initial validation.

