Rational/Approach. We will conduct a mixed method analysis to evaluate nursing workload and care delivery factors. Nursing care delivery factors including evaluation of CGM support, acceptance of CGM, perceived feasibility, and CGM knowledge, will be evaluated using a combination of questionnaires and focus groups.

Procedures/Variables and Measures. We will evaluate *nursing care delivery factors* related to CGM implementation support, acceptance of CGM, feasibility, appropriateness, CGM knowledge and satisfaction with CGM as measured by Acceptability of Intervention Measure (AIM), Intervention Appropriateness Measure (IAM), and Feasibility of Intervention Measure (FIM), CGM Satisfaction Questionnaire (modified for healthcare workers) and focus group conducted among nurses in the CGM-enabled MICU. The AIM, IAM, and FIM are brief 5 item Likert-scale questionnaires with each showing a high degree of content validity with alphas for the 3 questionnaires between 0.87 and 0.89.³⁰ CGM Satisfaction Questionnaire (CGM-SAT) is a 44-item measuring satisfaction with CGM over the previous 6 months. The survey has a high degree of validity ($\alpha \geq 0.94$) in adults with type 1 diabetes using CGM.³¹ Several items will be modified for application in healthcare workers. All MICU staff nurses (N=152) will be informed of the study and invited to participate via email. Upon e-consent, the questionnaires will be administered via a REDCap survey. A focus group will be conducted among MICU staff nurses (N=10) to gage their experience using CGM. A semi-structured interview guide will focus on areas of perceived CGM implementation support and education, CGM knowledge, and recommendations for future best practice. All Aim 2 variables and measures appear in Table 2.

RQ 3: To assess glycemic control among patients receiving CGM in the CGM enabled MICU compared to historical control patients who received POC glucose monitoring in the MICU.

Rational/Approach. We will analyze glycemic control factors among MICU patients on CGM compared to 100 historical control patients from the same MICU who receiving only POC glucose monitoring. We hypothesis that patients with CGM will exhibit greater time in range (100-180 mg/dl, 70-180mg/dl, 140-180mg/dl) and experience less frequent time in hypoglycemia than patients on fingerstick POC.

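### The RQ2 nurse survey does not record who cared for a study participant, so ratings of the study CGM protocol may be mixed with ratings of the unit's COVID-19 CGM protocol

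*Combined protocol and SAP*

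**What the plan says.** Section III.C, RQ 2 (Procedures/Variables and Measures), defines the survey population in one sentence: "All MICU staff nurses (N=152) will be informed of the study and invited to participate via email". The next step is equally open: "Upon e-consent, the questionnaires will be administered via a REDCap survey". The instruments are the AIM, IAM and FIM scales and the CGM-SAT, the last described as a "44-item measuring satisfaction with CGM over the previous 6 months". Several CGM-SAT items are to be adapted for healthcare workers; the plan does not say that any will name the study protocol.

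The focus group is defined in the same way: "A focus group will be conducted among MICU staff nurses (N=10) to gage their experience using CGM".

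The Nurse Participant Schedule of Activities lists a single administration and no variable for contact with study participants.

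On prior experience, section III.B says the MICU "has been utilizing Dexcom G6 CGM for COVID-19 patients since May of 2020", and the Nurse training paragraph in III.C says that "the protocol at use in this study differs somewhat from the COVID-19 protocol currently at use in the MICU". Current COVID-19 infection is an exclusion criterion, so CGM care of those patients is not care under the study protocol.

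**The concern.** RQ2 is meant to show how nurses view the CGM implementation under evaluation, and the primary objective in section I is the feasibility of CGM through a CGM+POC protocol. A nurse who has used CGM only with COVID-19 patients can complete every scale. So can a nurse who has used both protocols within the look-back, and nothing asks which one the answer describes.

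The two protocols differ in what they ask of the nurse. The study version has more frequent scheduled validation, added clinical events that trigger testing every 1 or 2 hours, and new criteria for ceasing clinical use of CGM. A mean feasibility or satisfaction score would be read as a statement about the study protocol, when an unknown part of it could concern the other one. The survey is given once, so an exposure item left out now cannot be added to the same answers later.

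**Working it through.** The plan gives no sample size, expected response rate or precision for RQ2, so there is no stated figure to reproduce. The check has three parts.

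**1. Are there two distinct protocols?** The CGM + POC Protocol text in section II gives ongoing validation every 6 hours for the existing protocol and every 4 hours for the study.
- Existing: 24/6 = 4 scheduled checks a day.
- Study: 24/4 = 6 a day, which is 50% more, before the event-triggered testing.

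**2. When does the survey fall?** In the Study Timeline (section III.A), the focus group and survey bars appear to start one column after patient recruitment and to end one column before it: three of its five columns, the second to the fourth. If that layout is right and accrual is even, the surveys run from about 20 to about 80 participants enrolled, and a 6-month recall could reach back before the study. The table may be damaged in extraction, so this is supporting evidence only.

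**3. What share of nurses would have no study participant?** Inputs from the documents are 152 nurses and 100 participants. Assumed: each participant is cared for by *k* distinct nurses chosen at random. After *P* participants, the expected unexposed share is (1 − k/152)^P.

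| Participants enrolled | k = 2 | k = 4 | k = 8 |
|---|---|---|---|
| 20 | 77% (117 nurses) | 59% (89) | 34% (52) |
| 40 | 59% (90) | 34% (52) | 12% (18) |
| 60 | 45% (69) | 20% (31) | 4% (6) |
| 80 | 35% (53) | 12% (18) | 1% (2) |
| 100 | 27% (40) | 7% (11) | 0.4% (1) |

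Uneven assignment of nurses would raise these shares.

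*Cross-check by assignments.*
- 48 beds at 1 nurse per 2 patients gives 24 assignments per shift.
- At 5 enrolments a week and an assumed MICU stay of 5 to 10 days, 5 × 5/7 = 3.6 to 5 × 10/7 = 7.1 participants are present at once.
- Since a nurse has at most one CGM patient, 3.6/24 = 15% to 7.1/24 = 30% of assignments involve a participant.
- Assume each nurse works one block of three shifts a week with the same patients. Enrolment takes 100/5 = 20 active weeks.
- Halfway, the unexposed share is 0.85^10 = 20% to 0.70^10 = 3%.
- At the end it is 0.85^20 = 4% to 0.70^20 = 0.1%.

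Both approaches give the same pattern: possibly large early, likely small by the end of recruitment. Neither addresses the second route to mixing, in which an exposed nurse also has COVID-19 CGM shifts inside the 6-month window.

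**The case against.** The strongest reply has five parts.

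- **Training and incidental contact.** The Nurse training paragraph has every nurse trained on the study protocol, including its differences from the COVID-19 one, before recruitment. Section III.C (RQ 1 procedures) has alarms that others can hear and expects another nurse to respond if the assigned one is busy. This stands as mitigation: a trained nurse can judge perceived feasibility. But training is not use, and answering an alarm is not a shift of 4-hourly validation.
- **Related experience.** RQ2 speaks of CGM implementation in general, and the existing protocol is also a CGM+POC protocol. This stands in part. COVID-19 experience is relevant, which is a reason to report it separately and not to discard it.
- **COVID-19 experience may be the smaller share.** Over 132 patients in about 24 months is about 132/24 = 5.5 a month, against 100/7 = 14 a month planned for the study. The first figure is a floor and admissions may be uneven, so this is indicative only.
- **Linkage.** The RQ3 model is to allow for nurse-level variability, so nurse identity per patient may be available to link with survey records. That is possible, but it is not planned, the patient schedule lists no nurse identifier, and linkage would not show which protocol an answer describes.
- **No decision depends on these scales.** No pilot benchmark, stopping rule or power calculation uses them, and RQ1 assesses implementation from the health record and recruitment log. This stands and limits the weight of the point.

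A reader might infer more: that the answers will reflect the COVID-19 protocol, and that they will be flattering because that protocol asks for less testing. The documents do not support either. The survey wording is not given, and the look-back is a description of the questionnaire before modification. Other features could push answers the other way: the COVID-19 cohort is described as extremely ill, and the study adds a nurses' station dashboard.

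**Conclusion.** The point holds in a limited form. As planned, RQ2 answers may mix views of two CGM protocols in use on the same unit, and no planned variable separates them. The unexposed share ranges from 34% to 77% after 20 participants to 0.4% to 27% after 100, for an assumed 2 to 8 nurses per participant. The low end of that staffing range looks unlikely for round-the-clock care, so the upper percentages are a pessimistic bound. No statement in the plan places the survey in the first 20 participants, so the early figures should not be read as the expected case. How much COVID-19 experience would lie inside the look-back, and the direction of any bias, are unknown.

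It might also be inferred that unexposed nurses must be barred from the survey. That does not follow. Unit-wide views are a legitimate implementation outcome, and a restriction alone would leave COVID-19 experience within the look-back of exposed nurses.

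**What to change.** Keep inviting all 152 nurses, and make four changes:

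1. Add two REDCap items: the number of shifts caring for a study participant, and the number of COVID-19 CGM shifts in the look-back period.
2. Word AIM, IAM, FIM and the CGM-SAT, which is being modified anyway, to refer to the study CGM+POC protocol since the nurse's first study participant.
3. Report RQ2 by exposure, with nurses who cared for at least one study participant as the main result and all respondents alongside.
4. Select focus-group nurses from those who cared for a study participant.

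The cost is two more survey items, a few sentences of protocol text and a somewhat smaller main analysis group. No invitations are withdrawn and no responses are lost.

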Sample Size Justification. The primary outcome for the power analysis is the percentage of time spent in target (70-180mg/dl). We estimate from previous studies^{13,28} that these values may have a standard deviation as high as 25 percentage points, in which case with 100 patients in each group we will have 80% power to detect a difference of 10 percentage points in time in range (e.g., 65 vs. 75); a moderate effect size of 0.4. If the standard deviation is lower (e.g., 15 as has been true in some studies), we will have greater power (99%) to detect a 10 point difference and are still well powered to detect smaller differences (e.g., 90% power for a 7 point difference). All power calculations assume an alpha of 0.05 and minimal statistical effects of clustering within the hospitals (e.g., unit or nurse level).

C. Detailed study procedures

Recruitment: Critical care clinical research coordinators will screen for preliminary eligibility and forward potential participant names to study team using a secure medical record in-basket process. The study team will determine eligibility. The study team will ask for permission for the patient to be approached. If permission is granted, the study team will verify eligibility and obtain informed consent from the patient or the patient's legally authorized representative. Consent will be obtained prior to research participation and CGM placement. Recruitment is expected at a rate of 5 patients per week over seven months. Our target recruitment will be 100 MICU patients.

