The patient will remain on CGM for the duration of their hospital stay and if discharged to home may transition to personal use of the Dexcom G6. The Dexcom G6 sensor is replaced every 10 days and will be removed and then replaced for some radiographic procedures or sensor failure. CGM data is automatically transferred to Dexcom's cloud-based Clarity system.

Table 3. OSUWMC Hypoglycemia Guideline, Patients Who are Not Alert, Are NPO, or on IV Insulin Infusion

Blood Glucose (BG) Level*	Action	Follow-Up
60-79 mg/dL	
 • Administer 7.5 g Dextrose D50% (15 ml) IV* • Consider calling House Officer if patient experiencing recurrent BG <70 mg/dL in past 12 h 	
 • Recheck BG q 15 min following treatment and treat accordingly until ≥ 80mg/dl • Once ≥ 80mg/dl, recheck BG q1h x2 (x4 if <45mg/dL at onset), then resume POC glucose as previously ordered, Patients who are admitted with hypoglycemia should be monitored at least q 4h for a minimum of 24h
45-59 mg/dL	
 • Administer 12.5 g Dextrose D50% (15 ml) IV* • Call House Officer to report BG and action taken 	
<45 mg/dL	
 • Administer 25 g Dextrose D50% (15 ml) IV* • Call House Officer to report BG and action taken 	
ALL	
 • Consider adding Dextrose 5% to maintenance IV fluids at a rate of ≥ 50ml/hr or increase rate of existing maintenance IV if dextrose source already present 	
 • If > 4h from initial event and BG ≥ 80mg/dl for two consecutive readings, may consider reducing IV dextrose

Variables and measures. *Clinical utility criteria:* Time to CGM validation within hybrid protocol parameters, mean percent of dosing decisions determined by CGM, changes in insulin dosing from standard guideline or outside standard times in response to alarm and/or trend data (as measured by manufacturer download data and corresponding EHR documentation). *Fidelity criteria:* Proportion of times CGM used non-adjunctively/number of

times non-adjunctive use indicated per protocol. *Adoption criteria:* Proportion of patients approached to received CGM monitoring/number of patients eligible to receive initial CGM monitoring.

RQ 2: To assess the degree to which CGM implementation within the ICU environment effects nursing workload and care delivery.

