Procedures. Glucose data will be directly transferred from the MICU patients (N=100) to Android mobile phones/Dexcom G6 app which captures and stores glucose values every 5 minutes (up to 288 values/day for 100% CGM wear). CGM data is automatically transferred from phones/Dexcom G6 app to Dexcom Clarity. Individual patient discrete data will be downloads directly from the Clarity site. Historical controls meeting the gateway criteria (glucose >250 mg/dl or on IV insulin during admission) from the same MICU will be matched on the following factors: Diagnosis and type of diabetes, home insulin use, steroid use during hospitalization, vasopressor use, North vs. South MICU wings (NP team floor vs. resident team floor, respectively), and diabetic ketoacidosis (DKA)/hyperosmolar hyperglycemic syndrome (HHS) status. POC glucose values for historical controls (N=100) will be obtained directly from OSUWMC EHR. EHR data will be obtained through an information warehouse request providing time stamped, POC glucose value for each match patient. All data will be uploaded into STATA 15.0 where it will be cleaned and merged prior to analysis.

Variables and Measures. Demographic, admission, and diabetes specific variables of interest appear in Table 2 and will be collected from the EHR for MICU participants and for historical controls. Clinical condition variables will include presence of renal replacement, mechanical ventilation, ECMO, associated cardiac arrest or cerebrovascular accident and SOFA score. SOFA score was calculated, though noted to have limited discriminant function for predicting mortality.³² The SOFA score has been validated in critically ill patients³³, and is currently the scoring system recommended by the Sepsis 3 definition.³⁴ CGM and POC glucose data will be aggregated into glucose ranges and thresholds as described in Table 2.

Exploratory aim:

RQ 4: To assess hospitalization outcomes and conduct economic evaluation of the costs to deliver CGM implementation in the MICU.

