Rational/Approach. We will explore the impact of CGM therapy using a CGM + POC protocol on patient hospital outcomes and costs. Analyzes the economic aspects inpatient CGM on patient health and healthcare interactions, with a focus on the costs (inputs) and consequences (outcomes) of CGM will enable full understanding of implementation effects. We hypothesize that patients with CGM will experience shorter length of stay, lower cost of stay, will be more likely to discharge to home vs. SNF, have a lower 30-day readmission rate, and experience lower mortality/morbidity than matched patients receiving fingerstick POC.

Procedures. Data will be retrospectively extracted from the EHR for patients using CGM in the MICU (N=100) along with 100 historical controls. Data will be obtained from the EHR and billing department through an information warehouse request. Data from the time in motion study will be evaluated to extrapolate the economic impact of nursing personnel time spent for CGM vs. POC glucose monitoring and resources used in POC vs. CGM glucose monitoring.

Variables and Measures. *Hospital outcomes criteria* include the following: Length of stay [ICU, total stay], cost of stay, discharge level of care [home, SNF], morbidity, mortality and readmission rate at 30 days. We will conduct economic evaluation of the costs to deliver CGM implementation in the MICU. We will track resources needed for CGM implementation including personnel, training, facilities, materials, equipment, and other necessary inputs. In addition to resources used, we will expand analysis to evaluate nursing productivity and burden. *Resource outcomes criteria* include: nursing time spent in CGM vs. POC glucose monitoring and cost of CGM vs. standard POC glucose monitoring materials.

Table 2. Patient Participant Schedule of Activities

Aim	Concept	Variable	Frequency	Measure	
Aim 1	Clinical utility criteria	Time to CGM validation (Aim 1 only)	Sensor placement (Q10 days)	
 • EHR • Clarity download 	
		Mean percent of dosing decisions determined by CGM	Daily		
		Changes in insulin dosing from guideline or outside standard times in response to alarm and/or trend data	Daily		
Aim 1	Fidelity & Adoption Implementation criteria	Proportion of times CGM initiated or patient approached for study inclusion according to protocol/total number of initiations	Admission	
 • EHR • Study recruitment log 	

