		Proportion of patients approached to received GCM monitoring/number of patients eligible to receive initial CGM monitoring	Admission		
		Acceptability of CGM			
		Appropriateness of CGM			
		Feasibility of CGM			
		CGM knowledge			
Aim 3	Patient condition	Demographic data: Age, race/ethnicity, gender	Admission	
 • EHR 	
		Height, weight, and BMI	Admission		
		Diagnosis and type of diabetes	Admission		
		Home diabetes regimen	Admission		
		Total daily insulin dose	Daily		
		Past medical history: tobacco use, COPD, hypertension, heart failure, coronary artery disease	Admission		
		Clinical condition: Admission/inpatient glucose, HbA1c, admission diagnosis, admitting service, MICU	Admission		

		location (North vs. South), DKA/HHS, sepsis, acute liver failure, acute heart failure		
		Clinical condition: SOFA score, dialysis, thromboembolic events, ECMO mechanical ventilation, ICU/hospital length of stay, cardiac arrest, cerebrovascular accident, mortality	Daily	
		Medications: vasopressor use, steroids, anticoagulants, acetaminophen dose	Daily	
		Creatinine, eGFR, ALT, AST, TBR, WBC, procalcitonin, ferritin, CRP, IL6, D-dimer, PTT, INR, troponin, pH, BHB, bicarbonate	Daily	
		Enteral or parenteral nutrition	Daily	
		O2 sat, pAO2, blood pressure	Daily	
Aim 3	Glycemic control	Time in target for CGM patients (70-180mg/dl)	Daily	
 • Clarity • EHR
		Time 100-180mg/dl for CGM patients	Daily	
		Time 140-180mg/dl for CGM patients	Daily	
		Time above range for CGM patients (>180mg/dl & >250mg/dl)	Daily	
		Time in hypoglycemia for CGM patients (<70mg/dl & <55mg/dl)	Daily	
		Percent POC in target (70-180mg/dl) (matched controls)	Daily	
		Percent POC 100-180mg/dl (matched controls)	Daily	
		Percent POC 140-180mg/dl (matched controls)	Daily	
		Percent POC above range (>180mg/dl & >250mg/dl) (matched controls)	Daily	
		Percent POC in hypoglycemia (<70mg/dl & <55mg/dl) (matched controls)	Daily	
		Glucose standard deviation	Daily	
		Glucose coefficient of variation	Daily	
Aim 4	Hospitalization outcomes and costs	Length of stay [ICU, total stay]	Discharge	
 • EHR • Clarity download
		Cost of stay	Discharge	
		Discharge level of care [home, SNF]	Discharge	
		Morbidity	Discharge	
		Mortality	Discharge	
		Readmission rate [30 days]	30d s/p discharge	
		Cost of CGM vs. standard POC glucose monitoring materials.	Discharge	

Table 3. Nurse Participant Schedule of Activities

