Any medical condition that is present at the time that the participant is screened will be considered as baseline and not reported as an AE. Participants are recruited from the MICU and are critically ill. Participants are not excluded based on the severity of critical illness and it is not uncommon for patients to deteriorate in the natural course of treatment or illness. If the study participant's condition deteriorates for reasons related to the study intervention (e.g., hypoglycemia) at any time during the study, it will be recorded as an AE.

Changes in the severity of an AE will be documented to allow an assessment of the duration of the event at each level of severity to be performed. AEs characterized as intermittent require documentation of onset and duration of each episode.

Adverse Event Reporting

Serious Adverse Event Reporting

The study investigator shall complete an Unanticipated Adverse Device Effect Form and submit to the reviewing Institutional Review Board (IRB) and the manufacturer as soon as possible, but in no event later than 10 working days after the investigator first learns of the effect. The study sponsor is responsible for conducting an evaluation of an unanticipated adverse device effect and shall report the results of such evaluation to the FDA and to all reviewing IRBs and participating investigators within 10 working days after the sponsor first receives notice of the effect. Thereafter, the sponsor shall submit such additional reports concerning the effect as FDA requests.

D. Unanticipated Problems

Definition of Unanticipated Problems (UP)

This definition could include an unanticipated adverse device effect, any serious adverse effect on health or safety or any life-threatening problem or death caused by, or associated with, the CGM intervention, if that effect, problem, or death was not previously identified in nature, severity, or degree of incidence in the investigational plan or application (including a supplementary plan or application), or any other unanticipated serious problem associated with a device that relates to the rights, safety, or welfare of subjects (21 CFR 812.3(s)).]

Unanticipated Problem Reporting

The investigator will report unanticipated problems (UPs) to the reviewing Institutional Review Board (IRB) and to the Data Coordinating Center (DCC)/lead principal investigator (PI). The UP report will include the following information:

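### RQ3 sets CGM glucose recorded only after sensor placement against POC glucose from historical controls who have no stated index time, observation window or exclusion list, so time in range can differ with no treatment effect

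*Combined protocol and SAP*

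**What the plan says.** **CGM group.** Section III.B finds patients by daily MICU screening for glucose above 250 mg/dl or current IV insulin, then applies ten exclusions. One is "Actively being treated for diabetic ketoacidosis (DKA"; another is refractory shock, defined by a vasopressor dose. Under Recruitment in III.C, "Consent will be obtained prior to research participation and CGM placement". RQ3 glucose for this group is the sensor download. On the end of wear, the RQ 1 procedures say "The patient will remain on CGM for the duration of their hospital stay".

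**Controls.** The RQ 3 procedures state: "Historical controls meeting the gateway criteria (glucose >250 mg/dl or on IV insulin during admission) from the same MICU will be matched". The six matching factors are diabetes diagnosis and type, home insulin, steroid use, vasopressor use, MICU wing and DKA/HHS status. The RQ 3 rationale adds that controls had POC monitoring only. Time-stamped POC values are pulled from the EHR, with no start or end given. In the patient schedule of activities, DKA/HHS is in a row collected at admission ("location (North vs. South), DKA/HHS, sepsis, acute liver failure, acute heart failure").

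**Analysis (III.D).** Daily and cumulative time in target are both assessed. The daily analysis keeps CGM days with at least 70% wear and control days with at least 3 fingersticks. A three-tier mixed model covers patient, unit and nurse variability. SOFA is collected in both groups but is named as a covariate only for RQ1.

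**Outcomes (RQ4).** "Data will be retrospectively extracted from the EHR for patients using CGM in the MICU (N=100) along with 100 historical controls".

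**The concern.** With historical controls, the rules on who enters and when the clock starts are the main protection against a spurious difference. Here they differ by group in three ways.

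- **Start.** A control's values from before qualifying, or between qualifying and a comparable placement time, can count. A CGM patient's cannot. The qualifying reading above 250 mg/dl is one such value.
- **Eligibility.** The CGM exclusions apply at enrolment, and nothing parallel is stated for controls.
- **End.** CGM runs through the hospital stay, RQ3 is worded as MICU care, and the end of control data is not given.

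Time in range (70-180 mg/dl) is the outcome that sized the study, and the hybrid II design gives effectiveness equal weight with implementation. Exploratory RQ4 has a related problem: CGM patients must survive and remain in the unit until placement, while controls need not.

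**Working it through.** **1. The plan's own figure.** Inputs from the Sample Size Justification: 100 per group, two-sided 0.05, difference 10 points, SD 25 (or 15). SE = SD × √(2/100) = 3.536 (SD 25) or 2.121 (SD 15). Normal-approximation power is 80.7% for 10 points at SD 25, 99.7% for 10 points at SD 15, and 91.0% for 7 points at SD 15. The stated 80%, 99% and 90% reproduce. The issue is bias, not sample size.

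**2. Does matching align the groups in time?**

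- DKA/HHS: the matching factor is a status collected at admission; the exclusion is active treatment at enrolment. A CGM patient enrolled after DKA treatment ends can be paired with a control whose POC values include the active episode.
- Vasopressors: matching is on use, with no dose or time; the exclusion is refractory shock.
- The other four factors carry no index time either, and the mixed model does not choose which part of the stay is sampled.

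**3. One extra pre-index day in controls only (illustration).** Assume no treatment effect, d later days, and an extra day that differs from them by 10 points (an assumed unit). Shift b = 10/(d+1). The two-sided rejection rate is 1 − Φ(1.96 − b/SE) + Φ(−1.96 − b/SE).

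- d = 3: b = 2.50; 10.9% (SD 25), 21.8% (SD 15)
- d = 5: b = 1.67; 7.6%, 12.3%
- d = 7: b = 1.25; 6.4%, 9.1%

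The shift can go either way. Time before qualifying has, by definition, no glucose above 250 mg/dl and no IV insulin, so it may be better than later time. Time between qualifying and a comparable placement may be worse.

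**4. The qualifying reading.** Take 72% in range otherwise (days 2-7 of the site's 19 COVID-19 patients, section II). One certain out-of-range reading in place of a typical one costs a control 72/(number of readings) points. Over an assumed 5 days this is 4.8 points at 3 readings a day (72/15), 2.4 at 6 a day (72/30) and 0.6 at 24 a day (72/120). It applies only to controls who qualify by glucose, overlaps with step 3, and should not be added to it.

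**5. The day filters.** Use the same cohort's 64% on day 1 and 72% on days 2-7, read day 1 as the first 24 hours of wear, and assume calendar days, d × 24 hours of wear from clock hour h, and no loss in controls. A first day with h > 7.2 (30% of 24) fails 70% wear; a last day with h < 16.8 also fails. Unfiltered mean = 72 − 8/d. The shift from filtering is:

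- h < 7.2: 8/d − 192/(24d − h)
- 7.2 < h < 16.8: 8/d − h/[3(d−1)]
- h > 16.8: 8/d − 8h/[24(d−1) + h]

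The worst case, every sensor placed just after 07:12, gives 8/d − 2.4/(d−1) = 1.47, 1.00 and 0.74 points for d = 3, 5 and 7. Averaged over uniform placement times, the shift is 0.31, 0.29 and 0.23 points, with rejection of about 5.1-5.2%, essentially nominal.

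**6. RQ4 sign check.** With assumed control mortality m = 0.30, share a of deaths and share b of survivors leaving before placement, CGM-group mortality is m(1−a)/[m(1−a) + (1−m)(1−b)].

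- a = 0.1, b = 0: 27.8%
- a = 0, b = 0.1: 32.3%
- a = b = 0.1: 30.0%

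The direction is open.

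**The case against.** The strongest reply is that controls are not unrestricted. Six matching factors and the POC-only limit were chosen for comparability, and DKA/HHS and vasopressor matching overlaps with the refractory shock, DKA and HONK exclusions. That stands, so it would be wrong to read the plan as making no attempt at comparability. The contrast is also not absolute. Under the stop-use rules in Table 1 and the nurse-training text, a CGM patient who newly develops DKA, HONK or refractory shock keeps the sensor for data collection, so CGM data can contain such periods. The difference lies in how patients enter. Matching narrows it without aligning time.

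A reader might infer three stronger things that the documents do not support.

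- **That the bias favours CGM.** Control time before qualifying may be better or worse than later time, and where control data end is unknown.
- **That the unequal day filters materially inflate false positives.** That needs nearly every sensor placed at the worst hour. Under uniform placement the effect is negligible, and the wear filter is stated for the daily measure only, not the cumulative one.
- **That RQ4 mortality must favour CGM because those patients survived to placement.** Early discharges can offset or reverse this, and RQ4 is exploratory.

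It is also fair that the size of the gap in the pre-index illustration is assumed.

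**Conclusion.** The point holds. As written, RQ3 can compare post-placement glucose in one group with any part of the stay in the other, and nothing in the matching or the model corrects this. Sign and size cannot be determined from the documents. The illustrated shift of 1.7 points (one extra day, 5 later days, 10-point gap) is small against the 10-point design effect. The rates of 7.6% and 12.3% rest on that assumed gap and on an independent two-sample test of patient means, whereas the plan uses matched controls and mixed models, so they are approximate. The 64% and 72% inputs come from 19 COVID-19 patients, a group excluded here, and may include some CGM effect. Aligning index, eligibility and window is a cheap improvement.

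**What to change.** - **Eligibility.** Apply to controls, at a defined index time, those III.B exclusions that the EHR can identify and that bear on severity or glycemia. First reconcile two statements: III.B says "patients with more severe illness and those with conditions that may interfere with CGM sensor accuracy will be excluded from participation", while IV.C says "Participants are not excluded based on the severity of critical illness".
- **Index.** Set the control index at the first qualifying glucose or IV insulin in the MICU plus the matched CGM patient's delay from qualifying to placement. Require the control to be alive and in the MICU then.
- **Window.** Use only post-index glucose in both groups, over the same care setting and in 24-hour periods from index. Set a common maximum number of days, because the plan itself hypothesises that CGM shortens ICU stay. Report the days each filter removes, by group.
- **RQ4.** Count length of stay and mortality from index.
- **Adjustment.** Adjust RQ3 and RQ4 for SOFA, glucose and IV insulin at index.

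Comparing POC values in both groups at a common sampling interval is an optional sensitivity analysis; it addresses sensor-versus-meter measurement, a separate issue.

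The cost is protocol and SAP wording and more EHR work, with no new patients. The downside is a smaller control pool. The 1,065 admissions in 2019 count glucose above 250 mg/dl only, before exclusions, matching and the alive-at-index rule; patients who qualify only by IV insulin would add to them. Check the usable pool first.
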